### 1.1 Objectives

Oral cancers will be biopsied by [name], [name], [name] and [name] and [name]. Precancerous oral lesions will be biopsied by [name]. For oral cancer/precancer patients biopsied at an outside institution and referred to Rutgers/University Hospital for care, outside H&E slides and unstained specimens for PDPN staining will be requested. [name] and [name] will evaluate tumor pathology, cell morphology, and PDPN expression in these patient samples. [name] will evaluate PDPN expression and MASL sensitivity from primary cultures of these cells. Study clinicians will evaluate oral cavity and health of their respective patients before and after MASL treatment. [name], [name], [name], [name], [name] or [name] will administer MASL dosage, evaluate any effects on oral structure and epithelium, and perform clinically indicated resection or biopsy to obtain specimen after treatment. [name], [name], [name], [name], [name] or [name] along with [name] and [name] will measure overall health before and after administration, and evaluate potential allergic reaction to MASL and respond to any unlikely scenarios. [name], [name] and [name] will evaluate pathology, cell morphology, and PDPN expression in these samples. We will determine if MASL treatment can decrease PDPN expression and normalize cell morphology in oral cancers and precancerous lesions.

Thus, primary, secondary, and tertiary objectives are as follows:

- a. Primary Objective: To evaluate and compare the morphology and podoplanin (PDPN) expression of cells included in the oral lesion initial biopsy to normal oral squamous epithelial cells (OSCCs).
- b. Secondary Objective: To evaluate and compare the PDPN expression of cells included in the resected oral lesion to normal oral squamous epithelial cells.
- c. Tertiary Objective: To evaluate and compare the morphology of cells included in the resected oral lesion to normal oral squamous epithelial cells.

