### 1.3 Primary, Secondary, and Tertiary Endpoints

Endpoints will be determined by cell morphology and PDPN expression examined by IHC. This work will be performed as an integral part of the study. The protocols rely on standard staining protocols to visual cells and PDPN expression with an approved antibody (D2-40). We have experience with this approach as previously described [56].

Our primary endpoint will be measured from patient biopsy material. We will compare the morphology and PDPN expression of cells included in the oral lesion to normal oral squamous epithelial cells. Patients eligible for the study will provide samples with lesion cells that are determined to be OSCC and express more PDPN than normal cells from the same sample specimen. In addition, these OSCC cells will express PDPN levels that are equivalent or greater than PDPN levels expressed by lymphatic endothelial cells (LECs) from the same specimen. Although this may be considered inclusion criteria, it is also an endpoint since these data will confirm that PDPN expression is increased in OSCC cells in our patient population. PDPN expression will be assessed by IHC for this endpoint since it can be used to qualitatively and quantitatively assess PDPN expression and be accomplished along with standard evaluations used for best care practice.

Our secondary endpoint will be measured from patient resection or second biopsy material. We will compare the PDPN expression of cells included in the oral lesion to normal oral squamous epithelial cells. Our secondary endpoint will be met if MASL treated OSCC cells express less PDPN than normal cells from the same sample specimen. In addition, these OSCC cells will express PDPN levels that are lower than PDPN levels expressed by lymphatic endothelial cells (LECs) from the same specimen. Our secondary endpoint will also require that the degree of PDPN expression decrease occurring after MASL administration is greater than any PDPN expression decrease observed after placebo administration. This comparison will be analyzed by t-test to achieve a p value less than 0.05.

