Our tertiary endpoint will be measured from the same patient resection or second biopsy material used to measure our secondary endpoint. We will compare the morphology of cells included in the oral lesion to normal oral squamous epithelial cells. Our tertiary endpoint will be met if MASL treated OSCC cells appear less dysplastic than they appeared before treatment. Dysplasia will be graded on a scale of 1 to 5, with 5 being the most dysplastic. Our hypothesis predicts that MASL treated OSCC cells will appear more cuboidal and flatter than they were before treatment.

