[name] and [name] will evaluate PDPN expression and cell morphology by IHC from formaldehyde fixed section of these samples. Surgical specimens will be fixed in 10% formalin in PBS, paraffin embedded, sectioned (4 microns), and processed for hematoxylin/eosin staining and immunohistochemistry D2-40 monoclonal antibody (Dako) to detect PDPN as described [56]. Paraffin-fixed specimens will be prepared by the local oral pathology laboratories at the University Hospital in Newark, NJ as part of the diagnostic histopathology. Routine pathology reports generated during patient care will also be examined to verify the tumor grade and nature of these specimens. Data will be examined by [name] and [name] in a blinded manner with coded labels such that they will not know whether the specimens are from MASL or placebo treated patients.

In addition to IHC analysis, [name] will establish primary cell cultures from these samples. He will evaluate cell morphology, assay PDPN expression by Western blotting, and evaluate the effects of MASL on the growth and migration of these cells by standard growth and motility assays [57]. This work will be performed at the Science Center in Stratford, NJ. Results from these studies will be used to elucidate understand how OSCC cells respond to MASL. However, these cell culture data will not be used as eligibility criteria since these assays may not be accomplished in a time frame consistent with treatment plans. The IHC analysis can be completed within 4 days. Therefore, this testing will not delay any subsequent treatment plans or options.

Patients with OSCC cells that express robust levels of PDPN will be considered for treatment. Robust levels of PDPN will be defined as greater than normal cells and equivalent or greater than PDPN levels expressed by lymphatic endothelial cells (LECs) from the same sample specimen. Patients that meet the eligibility criteria will be enrolled in the treatment phase of this study. Study clinicians ([name], [name], [name], [name], [name] or [name]) will administer MASL or placebo to enrolled subject. Patients will be given a lozenge (troche)with or without MASL added to achieve a final dosage of 100 mg per adult. Clinicians administering the lozenge and [name] are not blinded to the type of the lozenge; however, this information is not available to the pathologist who evaluates tumor pathology, cell morphology, and PDPN expression in the patient samples.

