In addition to the process described above, patients already diagnosed with oral cancer/precancer who present to one of the study clinicians for definitive care may also be enrolled in the study if they consent to participation. In these situations, it is routine to request H&E-stained slides from the original surgical pathology department for review as part of the surgical planning for clinical care. For patients who consent, the study clinician or PI would also request 1-3 unstained specimens for D2-40 staining to determine PDPN expression for research purposes. Patients with OSCC cells that express robust levels of PDPN and meet the eligibility criteria will be considered for treatment phase. The remainder of the protocol remains the same.

MASL and placebo lozenges will be prepared by an approved GMP certified facility by chromatography methods established by [name] as described [57]. Lozenges will be stored at the University Hospital Pharmacy and be hand delivered to the administering doctor by study investigators listed on page 1 in a sealed plastic container labeled with the patients name and ID. This work will be performed at the NJMS/RSDM/Rutgers Dental associates and University Hospital in Newark, NJ. [name], [name], [name], [name], [name] or [name] along with [name] and [name] will perform a general physical evaluation of their respective patients before and after MASL or placebo administration. [name] or [name] will

evaluate patient vital signs including temperature, pulse, blood pressure, and overall health after administration. [name] or [name] will also assist with management of any complication should it arise.

In this approach, MASL will find administration through topical exposure to oral lesions in the mouth as the lozenge dissolves. Patients will be asked to dissolve the lozenge in their mouth for at least 5 minutes before being chewed, and refrain from spitting, eating, or drinking for at least 20 minutes after lozenge administration. Subjects will be asked to finish chewing the lozenge within 20 minutes. Systemic exposure through the blood stream may also be accomplished. Data from university studies on cell lines and animal models indicate that MASL can be applied topically or eaten to target PDPN in order to inhibit tumor cell growth and migration. However, pharmacokinetics of this compound have not been established.

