### **3.3 Sample Size Justification**

We will recruit up to 10 patients for MASL treatment and 10 patients for placebo treatment to attempt a p value of less than 0.05 based on a difference of 40% with respect to Podoplanin expression and MASL sensitivity. Patients will be selected for treatment with MASL versus placebo by 1:1 randomization.

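### The tertiary success rule judges MASL on its own before-and-after dysplasia grade and leaves out the randomised placebo arm

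*Protocol*

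**What the plan says.** Protocol section 1.3 measures the tertiary endpoint on the resection or second-biopsy material and fixes when it succeeds: "Our tertiary endpoint will be met if MASL treated OSCC cells appear less dysplastic than they appeared before treatment". The scale is given: "Dysplasia will be graded on a scale of 1 to 5, with 5 being the most dysplastic". The same paragraph also announces a different comparison, "We will compare the morphology of cells included in the oral lesion to normal oral squamous epithelial cells", which matches the tertiary objective in section 1.1: "To evaluate and compare the morphology of cells included in the resected oral lesion to normal oral squamous epithelial cells".

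The secondary endpoint, defined just before it in section 1.3, is treated differently. There the fall in PDPN must be "greater than any PDPN expression decrease observed after placebo administration", tested by t-test at p below 0.05. That sentence covers PDPN only.

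On design, section 3.3 says "Patients will be selected for treatment with MASL versus placebo by 1:1 randomization", with up to 10 patients per arm. Section 3 has the pathology readers work from coded labels so that "they will not know whether the specimens are from MASL or placebo treated patients". For patients referred after diagnosis elsewhere, section 3 notes that "it is routine to request H&E-stained slides from the original surgical pathology department for review". Section 5 lists means, standard errors, t-test and ANOVA in general terms and ties none of them to dysplasia.

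**The concern.** A fall in grade within the MASL arm cannot be attributed to MASL without a control. The two specimens can differ for reasons unrelated to the drug. The first is a biopsy and the second a resection or another biopsy, so different tissue is sampled. For referred patients the first slides were prepared in an outside department. The stated blinding covers arm; masking of time point is not mentioned. Ordinary variation in reading a five-point grade adds to this. All of these influences act on placebo patients too, so the placebo arm would reveal them if the rule used it.

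The rule also leaves open whether it is judged patient by patient or on the arm mean, and how large a fall counts. Section 1.2 makes normalised morphology in vivo a stated hypothesis and section 7.3 commits to publication. At stake is a published claim that MASL improved morphology when nothing beyond chance or specimen differences occurred.

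**Working it through.** **Inputs from the protocol.** 10 MASL and 10 placebo patients (section 3.3, the stated maximum); integer grade 1 to 5 (section 1.3); success if the MASL grade is lower afterwards (section 1.3). The sample-size statement concerns PDPN expression and MASL sensitivity, so there is no stated figure for dysplasia to reproduce.

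**Assumed inputs.** The protocol gives no repeatability for the grade, so all variation below is assumed and shown as a range.

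**1. Arm-mean reading, exact, no drug effect.** Each of 10 patients falls one grade with probability q, rises one with probability q, and otherwise stays the same. With S the summed change, symmetry gives

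P(mean falls) = [1 − P(S = 0)] / 2, where P(S = 0) = Σₖ 10! / (k! k! (10 − 2k)!) · q²ᵏ (1 − 2q)¹⁰⁻²ᵏ.

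For q = 0.05 the terms are 0.3487 + 0.0969 + 0.0042 + 0.00004 = 0.4498, so P = (1 − 0.4498)/2 = 0.275.

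| Lesions regraded (2q) | P(mean falls) |
|---|---|
| 10% | 0.275 |
| 20% | 0.353 |
| 30% | 0.384 |
| 50% | 0.412 |
| 60% | 0.420 |

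**2. Arm-mean reading, simulation, no drug effect.** True grade normal with SD 0.7 and mean 3 to 4.5; two readings with error SD 0.3 to 0.8; values rounded and held within 1 to 5; 100,000 trials per scenario. P(mean falls) = 0.37 to 0.45.

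**3. Shift shared by both arms, still no drug effect.** Moving the second specimen down by 0.25 grade in the simulation gives P(mean falls) = 0.67 to 0.86. In the exact model, fall/rise probabilities of 0.25/0.15, 0.40/0.20, 0.30/0.10 and 0.45/0.15 give 0.60, 0.74, 0.79 and 0.86.

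**4. Other readings of the unit.**
- At least one patient improves, exact, no shift: 1 − (1 − q)¹⁰. For q = 0.05 this is 1 − 0.95¹⁰ = 0.40; for q = 0.30 it is 1 − 0.70¹⁰ = 0.97.
- More than half of patients improve: below 0.08 without shift, and about 0.02 to 0.18 with the 0.25-grade shift (simulation).

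**5. Using the placebo arm.** Change in grade compared between arms, 10 per arm, two-sided 0.05, counting only results that favour MASL:
- tie-corrected rank-sum test in the simulation: about 2%, with or without the shared shift;
- t-test in the model of step 1: 2.2% to 2.4%, including scenarios with a shared shift.

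**6. Power of that comparison (rank-sum, no shift).** 0.12 to 0.41 for a half-grade effect and 0.36 to 0.94 for a full grade, lowest where reading error is largest.

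**The case against.** **Matters for the SAP.** Test, alpha, unit and minimum change are often left to a SAP, and only the protocol was available. On an integer scale, a lower grade already means at least one step for a patient. This is fair for the details. It does not cover the main point, because the protocol itself states when the endpoint is met, and a SAP that required beating placebo would be changing that criterion.

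**The size depends on the reading.** The protocol never mentions a mean, and a more-than-half rule gives much smaller error rates (step 4). This stands, and the figures should be taken as illustrative. The arm-mean figures are not the extreme case, however: an any-patient reading gives 40% to 97%.

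**Normal-cell comparison and outside slides.** Normal epithelium could serve as the reference for assigning the grade, which would make the two comparisons compatible. Nothing says the outside department assigns the study grade. Both remarks are reasonable. What remains is that the protocol does not say how the normal-cell comparison enters the rule, and that specimen and preparation can still differ.

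**Existing safeguards and rank.** Placebo specimens are collected and read under coded labels, and nothing forbids reporting them. The endpoint is third in rank in a trial of up to 20 treated patients, and no stated decision depends on it. This limits the seriousness, but the success claim still ignores the control.

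**Conclusion.** The concern holds. The stated criterion can be satisfied without any drug effect, and no other part of the protocol supplies a placebo comparison for dysplasia. On the arm-mean reading the false-success rate is roughly 28% to 45% with no shift between specimens and 67% to 86% with a shared downward shift of 0.25 grade, against about 2% for a randomised comparison. These rates rest on assumed grading variation and an assumed shift, and other readings of the unit move them widely in both directions. That the rule omits placebo is certain; the size of the consequence is not. This should be corrected, but it is not critical, given the endpoint's rank and the trial's size.

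**What to change.** Choose one of two wordings in section 1.3:

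1. The endpoint is met if the reduction in blinded dysplasia grade from initial biopsy to second specimen is greater with MASL than with placebo, by Wilcoxon rank-sum test at a stated alpha, such as the 0.05 used for the secondary endpoint.
2. Remove the success rule and report change in grade by arm descriptively.

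In either case, state that specimens from both arms are graded 1 to 5 in the same way, and say in sections 1.1 and 1.3 how the comparison with normal cells relates to the chosen rule. Where stored slides allow, mask the reader to time point as well.

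The cost is mainly wording, since placebo specimens are already to be read under coded labels. Masking time point would mean re-reading some baseline slides, including outside ones, so it is optional. Option 1 makes the endpoint harder to claim, with the low power shown in step 6 of the working. Option 2 gives up a formal claim. At 10 per arm, low power is a reason to prefer option 2, not to keep an uncontrolled success rule.

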## 2. Background and Significance

Approximately 300,000 new cases of oral cancer are diagnosed each year, causing over 120,000 deaths worldwide [30,32]. Greater than 90% of these cancers are oral squamous cell carcinomas (OSCC) that proceed from hyperplasia to dysplasia, carcinoma in situ, and invasive carcinoma [55,27]. The potential for malignant progression of lesions including leukoplakia, erythroplakia, and leukoerythroplakia is primarily determined by the presence and degree of dysplasia [41,72,78,27].

Patients with early (stage I or II) OSCC are generally treated with surgery and radiation therapy, yielding 5-year survival rates between 70% and 95% [20,12,22,11,29,50,70,36]. However, patients with more advanced OSCC (stage III or IV) have much lower 5 year survival rates, ranging between 26% and 53% [54,66,69,36]. Metastasis to cervical lymph nodes is considered an extremely adverse prognostic factor for patients with OSCC [85,37,36]. OSCCs and premalignant lesions often exhibit polymorphisms in cyclin D1 and inactivation of tumor suppressors including p53, p16 and p14 [77,4,48,64,35,67,15,18,17,21,58,71]. Increased expression of tumor promoters including EGFR, c-myc, cyclin D1, TGF- $\alpha$ , and Pdpn are also often seen in such lesions [14,35,68,15,71,75,82]. Indeed, EGF signaling can induce PDPN expression in a number of OSCC cell lines [28].

PDPN expression is clearly associated with OSCC aggression, invasion, metastasis, postoperative recurrence, and poor survival. Taken together, reports indicate that PDPN

expression is notably increased in over 30% of precancerous oral lesions and in over 60% of oral cancers. Moreover, PDPN expression appears to correlate with oral cancer stage. About 50% of stage T1/T2 oral cancers display elevated PDPN expression levels, and this number increases to about 75% for stage T3/T4 oral cancers. In addition, over 70% of primary OSCC tumors that metastasize to lymph nodes express elevated PDPN levels. Clinical studies also indicate that 5 year overall survival rates continuously decrease from 93% for patients with weak podoplanin expression, to 47% for patients with moderate expression, to 23% for patients with high levels of podoplanin expression. OSCC recurrence also correlate very well, with undetectable, weak, moderate, and high PDPN expression resulting in 100%, 93%, 71%, and 51% disease free survival rates, respectively [49,85,8,37,16,23,36,27].

The bulk of the PDPN protein, about 150 amino acids, lies outside of the cell and could serve as an ideal target to combat cancer growth and progression [40,80]. For example, antibodies against PDPN and a PDPN interacting partner (tetraspanin CD9) can inhibit lung metastasis of CHO cells transfected with PDPN [34,53]. However, while antibodies may offer significant targeting specificity, they cannot be administered orally [3,9,31] and may not possess intrinsic pharmaceutical effects on melanoma cell growth and migration seen with orally available lectins.

We have shown that *Maackia amurensis* seed lectin (MASL) targets PDPN to inhibit tumor cell growth and motility [1,38,57]. The extracellular domain of PDPN is O-glycosylated with sialic acid,  $\alpha$ 2,3 linked to galactose [80]. PDPN is activated by endogenous lectins that bind to these extracellular carbohydrate moieties [73,5,7] to induce tumor cell motility and metastasis [81,83,84,73]. Thus, blocking this interaction should inhibit malignant progression. For instance, compounds blocking the action of galectins, which activate mucin receptors, can inhibit tumor cell metastasis [26,19].

Although some lectins may nonspecifically bind to many glycoproteins, MASL can precisely target specific glycoproteins expressed by human cells [47,46]. We have shown that MASL, which has a high affinity for O-linked carbohydrate chains containing sialic acid [76,25], binds to PDPN in order to inhibit tumor cell growth and motility at nanomolar concentrations. As we have recently reported, MASL can be taken orally to inhibit tumor growth in mice. Moreover, no side effects were evident from MASL ingestion based on animal weight, behavior, or organ morphology.

Lectins such as MASL offer significant medicinal value. Toxic lectins (e.g. ricin and viscumin) are extremely rare. In fact, lectins are found in virtually all foods [51,52]. In addition to carbohydrate modifications, lectin interactions are guided by amino acid residues of their target receptor proteins. Lectins can bind to their receptors with dissociation constants ( $K_d$ ) that rival the specificity of kinase inhibitors (e.g. lapatinib or imatinib) [33] and antibodies used against cancer (e.g. trastuzumab) [10,61,6,62]. For example, C-type lectin-like receptor 2 (CLEC-2) targets PDPN with an average dissociation constant ( $K_d$ ) of less than 4 nM [74]. In addition, unlike antibodies, lectins are resistant to gastrointestinal proteolysis [63,60,62] and can be taken orally to treat cancer [61,19,62]. Indeed, lectins can block the action of endogenous pro-metastatic lectins (such as galectins or selectins) to inhibit tumor cell growth [59-61], and can be used medicinally to treat cancer in people [62]. However, most anti-cancer lectins that have been examined thus far have intrinsically toxic ribosome inhibitory protein (RIP) activity similar to that of ricin, and target receptors that have not been identified [62]. Unlike these other lectins, MASL is not toxic to normal cells and targets a known receptor on cancer cells - PDPN.

As mentioned above, antisera may offer greater targeting specificity but lectins offer the advantage of oral administration. Dietary legumes (lentils, peas, or beans) have been shown to significantly lower the incidence of skin cancer [39]. Digestion of 200 grams of peanuts results in

concentrations of up to 200 nM of intact peanut lectin (PNA) in circulating blood [79]. Our Preliminary Studies and recently published data [57] indicate that similar concentrations of our model leguminous lectin, MASL, survive digestion, enter the circulatory system, and can effectively inhibit OSCC cell growth and migration.

Human safety for MASL has already been demonstrated as a “coincidental” component in traditional medicines used to treat ailments including cancer. *Maackia amurensis* has been used as a medicinal plant in Asia (called “Huai Huai” or “怀槐” in China) for several centuries [43,45,42,44,13]. It should also be noted that, although its targets and mechanisms are not yet defined, Mistletoe lectin (viscumin) binds proteins containing  $\alpha$ 2,3-sialic acid, has undergone clinical trials, and is widely used to treat melanoma in Europe [2,10,24]. However, human safety studies for MASL have not been reported.

We plan to utilize PDPN as a functionally relevant biomarker and chemotherapeutic target to combat oral cancer. For this project, oral cancers and precancerous lesions will be removed and examined for PDPN expression. Sensitivity to MASL, which targets PDPN on transformed cells, will be evaluated in fixed samples and primary cell cultures established from these specimens. MASL will then be orally administered to patients with lesions that contain cells that express PDPN and are sensitive to MASL. Samples from subsequent biopsies or resections, as determined by best care practices, will then be analyzed for PDPN expression and cell morphology. Overall oral and physical health will also be examined to evaluate the effects of MASL on each patient.

Thus, disease, investigation products, and rationale are as follows:

- a. Disease: oral cancer, specifically oral squamous cell carcinoma (OSCC).
- b. Investigational products: *Maackia amurensis* seed lectin (MASL).
- c. Rationale: MASL can be used as a nontoxic oral agent that targets the podoplanin (PDPN) receptor on OSCC cells topically and systemically to their growth, motility, and tumor progression.

